13.3.7 Hematologic

The following AE term, if considered Grade ≥ 3 or requiring dose modification or use of systemic steroids to treat the AE, are considered an ECI and should be reported to the Drug Manufacturer within 24 hours of the event:

- Autoimmune hemolytic anemia
- Aplastic anemia
- Disseminated Intravascular Coagulation (DIC)
- Haemolytic Uraemic Syndrome (HUS)
- Idiopathic (or immune) Thrombocytopenia Purpura (ITP)
- Thrombotic Thrombocytopenic Purpura (TTP)
- Any Grade 4 anemia regardless of underlying mechanism

All attempts should be made to rule out other causes such as metastases, sepsis and/or infection. Relevant diagnostic studies such as peripheral blood smear, reticulocyte count, LDH, haptoglobin, bone marrow biopsy or Coomb's test, etc., should be considered to confirm the diagnosis. However the AE should be reported regardless of etiology.

Course of Action

Grade 2 events:

- Report as ECI
- Hold pembrolizumab
- Prednisone 1-2 mg/kg daily may be indicated
- Consider Hematology consultation.
Permanently discontinue for inability to reduce corticosteroid dose to 10 mg or less of prednisone or equivalent per day within 12 weeks.

Grade 3 events:

- Report as ECI
- Hematology consultation.
- Hold pembrolizumab Discontinuation should be considered as per specific protocol guidance.
- Treat with methylprednisolone 125 mg iv or prednisone 1-2 mg/kg p.o. (or equivalent) as appropriate
- Permanently discontinue for inability to reduce corticosteroid dose to 10 mg or less of prednisone or equivalent per day within 12 weeks.

Grade 4 events:

- Report as ECI
- Hematology consultation
- Discontinue pembrolizumab for all solid tumor indications; refer to protocol for hematologic malignancies.

- Treat with methylprednisolone 125 mg iv or prednisone 1-2 mg/kg p.o. (or equivalent) as appropriate

13.3.8 Hepatic

The following AE terms, if considered \geq Grade 2 or greater (or any grade with dose modification or use of systemic steroids to treat the AE), are considered ECIs and should be reported to the Drug Manufacturer within 24 hours of the event:

- Autoimmune hepatitis
- Hepatitis
- Transaminase elevations

All attempts should be made to rule out other causes such as metastatic disease, infection or other hepatic diseases. However the AE should be reported regardless of etiology.

Drug Induced Liver Injury (DILI)

In addition, the event must be reported as a Drug Induced Liver Injury (DILI) ECI, if the patient meets the laboratory criteria for potential DILI defined as:

- An elevated alanine transaminase (ALT) or aspartate transaminase (AST) lab value that is greater than or equal to three times (3X) the upper limit of normal (ULN) and
- An elevated total bilirubin lab value that is greater than or equal to two times (2X) ULN and
- At the same time, an alkaline phosphatase (ALP) lab value that is less than 2X ULN,
- As a result of within-protocol-specific testing or unscheduled testing.

Note that any hepatic immune ECI meeting DILI criteria should only be reported once as a DILI event.

Course of Action

Grade 2 events:

- Report as ECI
- Hold pembrolizumab when AST or ALT >3.0 to 5.0 times ULN and/or total bilirubin >1.5 to 3.0 times ULN.
- Monitor liver function tests more frequently until returned to baseline values (consider weekly).
 - Treat with 0.5 - 1 mg/kg/day methylprednisolone or oral equivalent and when LFT returns to grade 1 or baseline, taper steroids over at least 1 month, consider prophylactic antibiotics for opportunistic infections, and resume pembrolizumab per protocol

- Permanently discontinue for inability to reduce corticosteroid dose to 10 mg or less of prednisone or equivalent per day within 12 weeks.
- Permanently discontinue pembrolizumab for patients with liver metastasis who begin treatment with Grade 2 elevation of AST or ALT, and AST or ALT increases $\geq 50\%$ relative to baseline and lasts ≥ 1 week.

Grade 3 events:

- Report as ECI
- Discontinue pembrolizumab when AST or ALT > 5.0 times ULN and/or total bilirubin > 3.0 times ULN.
- Consider appropriate consultation and liver biopsy to establish etiology of hepatic injury, if necessary
- Treat with high-dose intravenous glucocorticosteroids for 24 to 48 hours. When symptoms improve to Grade 1 or less, a steroid taper with dexamethasone 4 mg every 4 hours or prednisone at 1 to 2 mg/kg should be started and continued over no less than 4 weeks.
- If serum transaminase levels do not decrease 48 hours after initiation of systemic steroids, oral mycophenolate mofetil 500 mg every 12 hours may be given. Infliximab is not recommended due to its potential for hepatotoxicity.
- Several courses of steroid tapering may be necessary as symptoms may worsen when the steroid dose is decreased.
- Permanently discontinue for inability to reduce corticosteroid dose to 10 mg or less of prednisone or equivalent per day within 12 weeks.

Grade 4 events:

- Report as ECI
- Permanently discontinue pembrolizumab
- Manage patient as per Grade 3 above

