6.1.2 Subject Inclusion Criteria

In order to be eligible for participation in this trial, the subject must:

1. Be willing and able to provide written informed consent for the trial.
2. Be ≥ 18 years of age on the day of signing informed consent.
3. Have measurable disease based on RECIST 1.1 for peritoneal mesothelioma, and modified RECIST for pleural mesothelioma (Byrne et al 2004).
4. Have provided tissue from an archival tissue sample or newly obtained core or excisional biopsy of a tumor lesion. While 20 unstained slides or a tumor block are preferred, at least 14 unstained slides are requested for analysis. PI approval for a lower number of slides is acceptable.
5. Have a performance status of 0 or 1 on the ECOG Performance Scale.
6. Demonstrate adequate organ function as defined in Table 1, all screening labs should be performed within 14 days of treatment initiation.

Table 1 Adequate Organ Function Laboratory Values

System	Laboratory Value
Hematological	
Absolute neutrophil count (ANC)	$\geq 1,500$ /mcL
Platelets	$\geq 100,000$ / mcL
Hemoglobin	≥ 9 g/dL
Renal	

Serum creatinine OR Measured or calculated ^a creatinine clearance (GFR can also be used in place of creatinine or CrCl)	≤1.5 X upper limit of normal (ULN) OR ≥50 mL/min for subject with creatinine levels > 1.5 X institutional ULN
Hepatic	
Serum total bilirubin	≤ 1.5 X ULN OR
	Direct bilirubin ≤ ULN for subjects with total bilirubin levels > 1.5 ULN
AST (SGOT) and ALT (SGPT)	≤ 2.5 X ULN OR ≤ 5 X ULN for subjects with liver metastases
Coagulation	
International Normalized Ratio (INR) or Prothrombin Time (PT)	≤1.5 X ULN unless subject is receiving anticoagulant therapy as long as PT or PTT is within therapeutic range of intended use of anticoagulants
Activated Partial Thromboplastin Time (aPTT)	≤1.5 X ULN unless subject is receiving anticoagulant therapy as long as PT or PTT is within therapeutic range of intended use of anticoagulants
^a Creatinine clearance should be calculated per institutional standard.	

7. Female subjects of childbearing potential should have a negative urine or serum pregnancy within 72 hours prior to receiving the first dose of study medication. If the urine test is positive or cannot be confirmed as negative, a serum pregnancy test will be required.

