Diarrhea / Colitis	Grade 2 or 3	Withhold	
 • Administer corticosteroids (initial dose of 1-2 mg/kg prednisone or equivalent) followed by taper 	
 • Monitor participants for signs and symptoms of enterocolitis (ie, diarrhea, abdominal pain, blood or mucus in stool with or without fever) and of bowel perforation (ie, peritoneal signs and ileus). • Participants with \geq Grade 2 diarrhea suspecting colitis should consider GI consultation and performing endoscopy to rule out colitis. • Participants with diarrhea/colitis should be advised to drink liberal quantities of clear fluids. If sufficient oral fluid intake is not feasible, fluid and electrolytes should be substituted via IV infusion.
	Grade 4	Permanently discontinue		

AST / ALT elevation or Increased bilirubin	Grade 2	Withhold	
 Administer corticosteroids (initial dose of 0.5- 1 mg/kg prednisone or equivalent) followed by taper 	
 Monitor with liver function tests (consider weekly or more frequently until liver enzyme value returned to baseline or is stable)
	Grade 3 or 4	Permanently discontinue	
 Administer corticosteroids (initial dose of 1-2 mg/kg prednisone or equivalent) followed by taper 	
Type 1 diabetes mellitus (T1DM) or Hyperglycemia	Newly onset T1DM or Grade 3 or 4 hyperglycemia associated with evidence of β -cell failure	Withhold	
 Initiate insulin replacement therapy for participants with T1DM Administer anti-hyperglycemic in participants with hyperglycemia 	
 Monitor participants for hyperglycemia or other signs and symptoms of diabetes.
Hypophysitis	Grade 2	Withhold	
 Administer corticosteroids and initiate hormonal replacements as clinically indicated. 	
 Monitor for signs and symptoms of hypophysitis (including hypopituitarism and adrenal insufficiency)
	Grade 3 or 4	Withhold or permanently discontinue ¹		
Hyperthyroidism	Grade 2	Continue	
 Treat with non-selective beta-blockers (eg, propranolol) or thionamides as appropriate 	
 Monitor for signs and symptoms of thyroid disorders.
	Grade 3 or 4	Withhold or permanently discontinue ¹		

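### For patients admitted with raised liver tests, the hepatic rules do not say which stop limit applies after a drug-related rise, and they disagree on when treatment may resume

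*Combined protocol and SAP*

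**What the plan says.** **Entry.** Table 1 in Section 6.1.2 sets AST and ALT at "≤ 2.5 X ULN OR ≤ 5 X ULN for subjects with liver metastases". For bilirubin it accepts total bilirubin up to 1.5 × ULN or, as an alternative, "Direct bilirubin ≤ ULN for subjects with total bilirubin levels > 1.5 ULN". The alternative puts no upper limit on total bilirubin.

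**Hold and stop limits.** Section 13.3.8, under Grade 2 events: "Hold pembrolizumab when AST or ALT >3.0 to 5.0 times ULN and/or total bilirubin >1.5 to 3.0 times ULN". Under Grade 3 events, treatment is discontinued above 5.0 × ULN for AST or ALT, or above 3.0 × ULN for total bilirubin. Neither limit mentions baseline or liver metastases. The hepatic row of the immune-related AE table in Section 6.2.1.2 has the same structure: "AST / ALT elevation or Increased bilirubin Grade 2 Withhold", then permanent discontinuation at Grade 3 or 4, with no liver-metastasis variant.

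**Special line.** Also under Grade 2 events in 13.3.8: "Permanently discontinue pembrolizumab for patients with liver metastasis who begin treatment with Grade 2 elevation of AST or ALT", when AST or ALT rises by at least 50% over baseline and the rise lasts at least one week. Bilirubin has no counterpart.

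**Restarting.** The general dose-modification table in 6.2.1.2 accepts resolution to Grade 0-1 or to baseline. Section 13.3.8 accepts Grade 1 or baseline as the point at which steroids are tapered and treatment then resumes as the protocol directs. The general instructions above the immune-related AE table require Grade 1 or 0, and permanent discontinuation if the event has not resolved within 12 weeks of the last dose.

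**Scope.** The general table covers drug-related events, the second table covers immune-related events, and Section 13.3.1 confines the management guidance to events the physician judges related.

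**The concern.** The protocol deliberately admits some patients whose liver tests already lie at levels the hepatic rules call Grade 2. For them, a limit set against ULN and a limit set against their own baseline are different limits. The document uses both, for stopping and for restarting, without saying which applies to this group.

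What is at stake is consistent handling. After a drug-related rise, two physicians could read different lines and reach different decisions on whether the patient may restart, or on whether the fixed limit applies to a patient covered by the special line. That affects patient safety and how long the patient is treated.

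**Working it through.** There is no sample size or power figure to reproduce here. The check is threshold arithmetic plus a comparison of sections.

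**1. Who is admitted inside the hold band**

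- AST/ALT: the liver-metastasis allowance extends entry from 2.5 to 5.0 × ULN. The hold band is >3.0 to 5.0, so it covers (5.0 − 3.0)/(5.0 − 2.5) = 80% of the width of that extension. Values >2.5 to 3.0 are outside it. No patient can enter above the 5.0 × ULN stop limit.
- Bilirubin: every patient using the direct-bilirubin alternative has total bilirubin above 1.5 × ULN. That is numerically in the hold band, or in the stop band if the total exceeds 3.0 × ULN.

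These are positions on the scale, not triggers. Under the scope statements an unchanged entry value does not start the rules.

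**2. Which stop limit is met first**

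Let b be one enzyme's baseline in multiples of ULN, with 3.0 < b ≤ 5.0. The special line needs 1.5 × b for at least a week. The fixed line needs any value above 5.0, with no minimum duration. The fixed line is met first when 1.5 × b > 5.0, that is, when b > 5.0/1.5 = 3.33.

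| Baseline (× ULN) | 1.5 × baseline | Rise that reaches 5.0 × ULN | Result |
|---|---|---|---|
| 3.2 | 4.80 | 56.2% | special line can be met below the fixed limit |
| 3.33 | 5.00 | 50.0% | crossover |
| 3.5 | 5.25 | 42.9% | fixed line first |
| 4.0 | 6.00 | 25.0% | fixed line first |
| 4.5 | 6.75 | 11.1% | fixed line first |
| 4.8 | 7.20 | 4.2% | fixed line first |
| 5.0 | 7.50 | any rise | fixed line first |

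Share of the Grade 2 range above the crossover: (5.0 − 3.33)/(5.0 − 3.0) = 1.67/2.0 = 83%.

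**3. From share of range to share of patients**

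The documents give no distribution of baseline values, so this step rests on assumptions. A uniform spread over 3.0 to 5.0 gives 83%. If the density falls exponentially at rate λ per ULN unit, the share is (e^(−λ/3) − e^(−2λ))/(1 − e^(−2λ)):

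| λ | 0.5 | 1.0 | 1.5 | 2.0 | 2.5 |
|---|---|---|---|---|---|
| Share above 3.33 | 76% | 67% | 59% | 50% | 43% |

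**4. Restarting, for a patient admitted at AST 4.0 × ULN who has a related rise, is held, and returns to 4.0**

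- General table, 6.2.1.2: back at baseline, so restart is allowed.
- 13.3.8: back at baseline, so steroids are tapered and treatment resumes as the protocol directs.
- Immune-related AE instructions, 6.2.1.2: 4.0 × ULN is still in the Grade 2 band, so restart is not allowed. Unless the value falls below where the patient began, the 12-week clause leads to permanent discontinuation.

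The same laboratory value gets different answers. The same reasoning applies to a patient admitted at total bilirubin 2.0 × ULN with normal direct bilirubin.

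**The case against.** The strongest objection concerns the two stop lines. Both say only to discontinue. Neither tells the physician to continue until a 50% rise, and neither exempts anyone from the Grade 3 limit. They can be applied together, stopping at whichever is met first. This stands. A reader might infer that the protocol gives opposite continue and stop answers for the same enzyme value; the text does not support that. What remains is that, read together, the 50% and one-week conditions have little effect above 3.33 × ULN, and nothing says whether that was intended.

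A reader might also infer that the special line never decides above 3.33 × ULN. That assumes one enzyme. The line refers to AST or ALT in both its halves. Read literally, a patient with AST stable at 4.5 × ULN and ALT rising from 1.2 to 1.8 × ULN (1.2 × 1.5) for a week meets the special line but not the fixed one. The line also decides for baselines >3.0 to 3.33.

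A third tempting reading is that these patients must be held from the first dose. The scope statements rule it out: an unchanged entry value is not a drug-related event.

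Finally, Section 13.3.1 calls its recommendations guidelines, leaves room for clinical judgment, and defers to the protocol's own language on dose modification. That does not settle restarting, because the two tables that disagree are both in Section 6.2.1.2. One could argue that the immune-related table governs immune-related events. But 13.3.8 is also guidance on such events and names baseline. The text after the general table adds another difference: with the PI's agreement, an asymptomatic and controlled laboratory event still at Grade 2 after 12 weeks may continue. The immune-related instructions contain no such exception for hepatic events.

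**Conclusion.** The concern holds as a minor one, in two parts, and only once a drug-related or immune-related rise has occurred.

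1. For a single enzyme with baseline above 3.33 and up to 5.0 × ULN, the fixed stop limit is met before the liver-metastasis line, and the relation between the two is not stated. This is ambiguity, not contradiction. The 83% is a share of the Grade 2 range and should not be read as a share of patients.
2. The restart conditions contradict each other for a patient whose baseline is already Grade 2. This is the firmer part and needs no distributional assumption.

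The documents do not give the number of patients with liver metastases and raised enzymes, or with isolated raised total bilirubin. It is probably small. A reader might infer a threat to the Part A decision, which turns on 3 responses in 35. The documents do not show one: the number affected is unknown, and Section 6.11 keeps every treated patient evaluable.

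**What to change.** Reconcile Table 1 in Section 6.1.2, both tables and the accompanying instructions in Section 6.2.1.2, and Section 13.3.8. For patients admitted with values above the hold level:

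- state one reference, ULN or the patient's own baseline, for the hold, restart and stop limits, covering bilirubin as well as AST/ALT;
- state whether the liver-metastasis line adds to the Grade 3 line or replaces it, and whether its 50% rise must be in the enzyme that was raised at entry;
- use the same restart condition and the same 12-week condition in all three places.

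The clinical team decides which reference and which rule apply; no threshold is proposed here. The cost is wording in the next amendment. No extra tests are needed, because baseline liver values are already collected at screening.

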13.3.9 Neurologic

The following AE terms, regardless of grade, are considered ECIs and should be reported to the Drug Manufacturer within 24 hours of the event:

- Autoimmune neuropathy
- Demyelinating polyneuropathy
- Guillain-Barre syndrome
- Myasthenic syndrome

All attempts should be made to rule out other causes such as metastatic disease, other medications or infectious causes. However the AE should be reported regardless of etiology.

Course of Action

Grade 2 events:

- Report as ECI
- Moderate (Grade 2) – consider withholding pembrolizumab.
- Consider treatment with prednisone 1-2 mg/kg p.o. daily as appropriate
- Consider Neurology consultation. Consider biopsy for confirmation of diagnosis.
- Permanently discontinue for inability to reduce corticosteroid dose to 10 mg or less of prednisone or equivalent per day within 12 weeks.

Grade 3 and 4 events:

- Report as ECI
- Discontinue pembrolizumab
- Obtain neurology consultation. Consider biopsy for confirmation of diagnosis
- Treat with systemic corticosteroids at a dose of 1 to 2 mg/kg prednisone or equivalent once per day. If condition worsens consider IVIG or other immunosuppressive therapies as per local guidelines

When symptoms improve to Grade 1 or less, steroid taper should be started and continued over no less than 4 weeks

13.3.10 Ocular

The following AE terms, if considered Grade ≥ 2 or requiring dose modification **or use of systemic steroids to treat the AE**, is considered an ECI and should be reported to the Drug Manufacturer within 24 hours of the event:

- Uveitis
- Iritis

All attempts should be made to rule out other causes such as metastatic disease, infection or other ocular disease (e.g. glaucoma or cataracts). However the AE should be reported regardless of etiology.

Course of Action

Grade 2 events:

- Evaluation by an ophthalmologist is strongly recommended.
- Treat with topical steroids such as 1% prednisolone acetate suspension and iridocyclitics.
- Discontinue pembrolizumab as per protocol if symptoms persist despite treatment with topical immunosuppressive therapy.

Grade 3 events:

- Evaluation by an ophthalmologist is strongly recommended
- Hold pembrolizumab and consider permanent discontinuation as per specific protocol guidance.
- Treat with systemic corticosteroids such as prednisone at a dose of 1 to 2 mg/kg per day. When symptoms improve to Grade 1 or less, steroid taper should be started and continued over no less than 4 weeks.
- Permanently discontinue for inability to reduce corticosteroid dose to 10 mg or less of prednisone or equivalent per day within 12 weeks.

Grade 4 events:

- Evaluation by an ophthalmologist is strongly recommended
- Permanently discontinue pembrolizumab.
- Treat with corticosteroids as per Grade 3 above

13.3.11 Renal

The following AEs if \geq Grade 2 are considered ECIs and should be reported to the Drug Manufacturer within 24 hours of the event:

- Nephritis
- Nephritis autoimmune
- Renal failure
- Renal failure acute

Creatinine elevations \geq Grade 3 or any grade with dose modification or use of systemic steroids to treat the AE.

All attempts should be made to rule out other causes such as obstructive uropathy, progression of disease, or injury due to other chemotherapy agents. A renal consultation is recommended. However the AE should be reported regardless of etiology.

Course of Action

Grade 2 events:

- Hold pembrolizumab
- Treatment with prednisone 1-2 mg/kg p.o. daily.
- Permanently discontinue for inability to reduce corticosteroid dose to 10 mg or less of prednisone or equivalent per day within 12 weeks.

Grade 3-4 events:

- Discontinue pembrolizumab
- Renal consultation with consideration of ultrasound and/or biopsy as appropriate
- Treat with systemic corticosteroids at a dose of 1 to 2 mg/kg prednisone IV or equivalent once per day.

When symptoms improve to Grade 1 or less, steroid taper should be started and continued over no less than 4 weeks.

13.3.12 Skin

Rash and Pruritus

The following AEs should be considered as ECIs, if \geq Grade 3 and should be reported to the Drug Manufacturer within 24 hours of the event:

- Pruritus
- Rash
- Rash generalized
- Rash maculo-papular
- In addition to CTCAE Grade 3 rash, any rash that is considered clinically significant, in the physician's judgment, should be treated as an ECI. Clinical significance is left to the physician to determine, and could possibly include rashes such as the following:
 - rash with a duration >2 weeks; OR
 - rash that is $>10\%$ body surface area; OR
 - rash that causes significant discomfort not relieved by topical medication or temporary cessation of study drug.

Other Skin ECIs

The following AEs should **always** be reported as ECIs, regardless of grade, and should be reported to the Drug Manufacturer within 24 hours of the event:

- Dermatitis exfoliative
- Erythema multiforme
- Steven’s Johnson syndrome
- Toxic epidermal necrolysis

Please note, the AE should be reported regardless of etiology.

Course of Action

Grade 2 events:

- Symptomatic treatment should be given such as topical glucocorticosteroids (e.g., betamethasone 0.1% cream or hydrocortisone 1%) or urea-containing creams in combination with oral anti-pruritics (e.g., diphenhydramine HCl or hydroxyzine HCl).
- Treatment with oral steroids is at physician’s discretion for Grade 2 events.

Grade 3 events:

- Hold pembrolizumab.
- Consider Dermatology Consultation and biopsy for confirmation of diagnosis.
- Treatment with oral steroids is recommended, starting with 1 mg/kg prednisone or equivalent once per day or dexamethasone 4 mg four times orally daily. When symptoms improve to Grade 1 or less, steroid taper should be started and continued over no less than 4 weeks.
- Permanently discontinue for inability to reduce corticosteroid dose to 10 mg or less of prednisone or equivalent per day within 12 weeks.

Grade 4 events:

- Permanently discontinue pembrolizumab.
- Dermatology consultation and consideration of biopsy and clinical dermatology photograph.
- Initiate steroids at 1 to 2 mg/kg prednisone or equivalent. When symptoms improve to Grade 1 or less, steroid taper should be started and continued over no less than 4 weeks.

